The cued go/no-go (CGNG) task is an ideal choice for in-the-moment impairment feedback. Its instructions are simple; practice effects are minimal; and is sensitive to alcohol^{22-31,39}. The CGNG tests ability to respond fast to “go” targets (activation) while withholding response to “no-go” targets (inhibition). Activation/inhibition tension is externally valid. Dual process models⁴⁰⁻⁴³ posit risk behaviors stem from overactive appetitive drives that are compelling and hard to inhibit. Poor CGNG performance post-alcohol has been related to poor simulated driving, enhancing external validity⁴⁴. Moderate dosing to .05-.06% BAC reliably increases inhibition errors⁴⁵⁻⁵¹, but slowing reaction time (RT) to “go” cues requires higher doses^{44, 46, 47, 52}. RT to go cues often recovers later in a drinking episode (acute tolerance⁵³) but ability to inhibit does not. Thus at this BAC, ability to respond remains but inhibition is impaired, which relates to risk behaviors like DUI as young adults underrate impairment¹⁷.

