| 5:45 | Breath alcohol (BrAC) reading, use app, self-report of perceived impairment & other measures, then BrAC |
| 6:15 | 1-hour free-drinking period when participants can self-administer more vodka mixed drinks to max BAC=.12% |
| 7:15 | Participant drinks small glass of water to rinse alcohol from mouth, then BrAC |
| 7:45 | BrAC, use app, all participants will get feedback on performance, self-reported impairment/other measures |
| 8pm | Food provided, participants' phones returned and staff extracts data from study phones. |
| 10pm | Usability ratings of assigned app, 4-week field period explained, experimental feedback app provided to all |
| 11pm | Earliest possible dismissal once BrAC \leq .02% |

App condition: The control version is a smartphone-compatible CGNG. Each trial has this order: fixation cross (250ms); blank (250ms), vertical or horizontal cue (white rectangle) for 1 of 6 stimulus onset asynchronies (100, 200, 300, 400, 500, 750ms); go or no-go target (green or blue rectangle, respectively) until participant responds or 500ms; inter-trial interval (250ms). Participants are told to respond fast to green, not to blue. Cues signal a target at 70% probability (horizontal: go, vertical: no-go). Activation and inhibitory tendencies develop cue-dependence^{70, 71}. Go cues speed RT to go targets, which must be overcome for no-go targets.

Inhibition errors are more common after go cues. The app is the same as a computer version except it fits a smartphone (Fig. 2b) with instructions to press the screen directly rather than a keyboard and includes 75, not 250 trials.

The standard version is the same as the control version with the exception that information about performance (correct or incorrect) is displayed along with RT in ms for a correct response during each inter-trial interval.

[figure not shown]

Figure 3. *Example* partial Decision Tree for CGNG Experimental Feedback App use

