The experimental, feedback version includes the standard plus feedback on RT and inhibition errors compared to pre-drinking (Fig. 3). Based on past findings⁴⁵⁻⁵¹, if they react >20 ms slower and/or make $>5\%$ errors, they will get a message summarizing the performance decrement and implications for an outcome, picked randomly among trouble driving, risky sex, drug use, delinquency, or aggression. The app will state that there are simple alternatives with invitation to press a box to view advice, based on research that risk information may increase risky behavior if convenient options are not given⁷². Feedback will be worded non-judgmentally per motivational interviewing tenets.

Post-session field use:

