Normal probability plots will be reviewed to assess normality and need for transformations. Paired samples *t*-tests will be used to confirm an effect of initial dose on CGNG inhibition errors but not RT. Our analytic strategy will resemble 3 past studies. The main method will be multiple regression with study condition and sex as predictors. Baseline variables that differ significantly by condition will be covaried.

Outcome 1a will be BAC during self-administration. Because we will not interrupt alcohol self-administration with BrAC readings, we will calculate peak estimated BAC (eBAC) based on number of alcoholic drinks, time elapsed, weight and sex. eBAC was sensitive to differences in consumption between study conditions in a prior study conducted by [name]. Results will be BrAC-confirmed after the 1-hr free-drinking period. Though not the main focus, we will test 2-way interactions of study condition by RT and inhibition errors post-alcohol to see if more inhibition failures under alcohol predict self-administration. Regressions will be confirmed using multilevel models (MLM) in Mplus with random effect of group (people completing a drinking session together) and other predictors as fixed effects. Since participants will be randomized to different apps, we do not expect strong intra-class correlations, which should result in similar findings in regression and MLMs. In our in-progress study, no group level effects have emerged. A similar strategy will be used for 1b (alcoholic drinks self-administered).

Primary Aim 2 will entail comparisons of alcoholic drinks consumed per occasion between the 2 weeks participants will use vs. not use the app in the 4-week field period post-drinking session. We will retain study condition as a predictor (effects of lab-assigned condition are not hypothesized here) and a random group effect while adding app use vs. non-use period as a within-subjects effect in MLM. ANOVA will compare usability and acceptability ratings at the end of the drinking session and 4-week field period across app conditions. For mediation (Secondary Aim), we will test for indirect effects of app condition on self-administration via perceived impairment using MacKinnon’s products of coefficients approach with bootstrapped confidence intervals (CIs). This approach accounts for non-normality of the product of

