Our goal was to power the study for the Primary and Secondary Aims. Roberts and Fillmore's findings speak to the potential impact of task-based feedback (Preliminary Study 5 [PS5]). Perceived ability to drive post-alcohol declined from $M=46.8(4.7)$ to $29.7(5.5)$ in the higher risk DUI group and only $M=25.8(5.5)$ to $21.2(4.8)$ in the no-DUI group: a large effect difference ($d=1.5$). While not the same as a control condition, the no-DUIs were a subgroup in which the intervention had minimal impact, as with a control condition. Our alcohol study in-progress (Preliminary Study 1 [PS1]) is relevant as a test of effects of an app on alcohol self-administration though the methods are not identical. Since our ongoing study does not begin with a fixed dose targeting a specific BAC, results involving number of alcoholic drinks self-administered are more comparable to the proposed study and more appropriate for power and effect size estimation. In our in-progress study, the smartphone breathalyzer device/app was associated with significantly less alcohol self-administration ($M=3.5$ drinks, $SD=1.3$) than a control condition ($M=4.8$, $SD=1.5$), $d=.89$. Considering these findings, we project a large effect size.

Aim 1 power is based on ability to detect a between-subjects effect of app condition. We used an effect size equivalent to our in-process smartphone breathalyzer study for effect of condition (experimental vs. control groups). This estimated effect is much smaller than in Roberts and Fillmore's prior study providing feedback regarding cognitive impairment to a sample of drinkers with and without a prior DUI. Assuming an effect ($d=.89$) at $\alpha=.025$ (to account for comparisons between the experimental app and each of the other study conditions: standard and control), the proposed sample of 99 completing the lab session and follow-up period yields .90 power. For Primary Aim 2, the goal will be to compare alcohol use in the 2 weeks participants use vs. do

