not use the experimental app. No study condition effect is hypothesized, thus the focus will be on within-subjects comparison. As such, assuming $\alpha=.05$ at 90% power, we can detect an effect of .33 (small-to-medium). The secondary aim of testing the indirect effect of app condition on drinking via perceived impairment will require the largest sample size as it entails tests of between group differences and tests of indirect effects are underpowered relative to tests of direct effects. In a Monte Carlo simulation, assuming small-to-medium correlation (.35) between perceived impairment and drinks self-administered (DV), power to detect an effect of the IV (study condition) on the mediator and an effect of the mediator on the outcome was $>.90$ and power to detect an indirect effect was .80 with 33 per condition (N=99 total).

7. Possible Discomforts and Risks

Potential risks in this study were identified in accordance with the recommended guidelines on ethyl alcohol administration in human experimentation put forth by the National Advisory Council on Alcohol Abuse and Alcoholism (2005) and two reviews on this subject (Dolinsky & Babor, 1997; Wood & Sher, 2000). Steps taken to minimize these risks were also developed in accordance with these documents.

Alcohol consumption: A number of medical conditions could potentially be worsened by acute alcohol administration (e.g., liver disease, cardiac abnormality, pancreatitis, diabetes, neurological problems, and gastrointestinal disorders). As a result, participants with such medical problems as revealed by a medical history taken during the in-person screening will be excluded from the study.

Alcohol self-administration in a research study by individuals who are severely alcohol dependent as evidenced by current withdrawal or a history of withdrawal may pose a risk to their health and safety. Alcohol self-administration in a research study by individuals who are seeking treatment for alcohol use disorder or who have recently engaged in intensive treatment for alcohol dependence may compromise their efforts to reach or to maintain abstinence or moderate levels of alcohol use.

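### A non-significant paired t-test cannot show that the fixed dose leaves reaction time unaffected: a minor flaw in a dose check on which no aim depends

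*Combined protocol and SAP*

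**What the plan says.** Section 6, Data analyses, opens with a check of the fixed alcohol dose: paired-samples t-tests "will be used to confirm an effect of initial dose on CGNG inhibition errors but not RT". The text does not say whether the initial dose means the individual session, the group session or both.

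The expectation comes from section 4, Background, which argues from cited studies of the cued go/no-go (CGNG) task: "Thus at this BAC, ability to respond remains but inhibition is impaired".

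The only size of RT change given any meaning in the document is in section 6, App condition. There the experimental app sends a participant a message about a performance decrement "if they react >20 ms slower and/or make" more than 5% errors. That is a feedback trigger and is not linked to the t-test.

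The document gives no equivalence margin, no confidence-interval criterion, no SD for RT change and no power for the RT comparison.

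**The concern.** One kind of test is asked to support two opposite claims. A significant result supports an effect on errors. To support no effect on RT, the same procedure has to return a non-significant result, and a small or noisy data set makes that more likely. Two features of the design bear on noise. The app version of the task "includes 75, not 250 trials". Section 6, Overview, also allows some participants to do the field period only, so fewer than 99 may contribute lab data.

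At stake is one descriptive statement in the report: that in this sample the dose impaired inhibition and left speed of responding intact. RT could be described as unaffected after a mean slowing as large as the amount for which the app warns an individual.

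**Working it through.** **Inputs from the document**
- N=99, from Sample, power & effect size: "the proposed sample of 99 completing the lab session and follow-up period yields .90 power".
- Alpha .05, the value given there for the within-subject comparison. Sidedness is not stated; two-sided is used here.
- 20 ms, the app's feedback trigger, used only as a benchmark for a slowing that matters.

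**Assumed, because not given:** the SD of the pre-to-post RT change, 40 to 100 ms, and a reduced lab sample of 50 for illustration.

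**Step 1. Reproduce the plan's own paired figure.** For Primary Aim 2 the plan states a detectable within-subject effect of .33 at 90% power. For a paired t-test the noncentrality is dz × √N, where dz is the mean change divided by the SD of the change.
- Normal approximation: (1.960 + 1.282)/√99 = 0.326.
- Noncentral t with 98 df: detectable dz = 0.329, and power at dz = .33 is 0.902.

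The stated .33 reproduces with a two-sided test, so the same method is applied to RT.

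**Step 2. Chance that a true 20 ms mean slowing is non-significant.** Here dz = 20/SD. The noncentrality at N=99 is dz × √99 = dz × 9.950, and the critical t is 1.984.

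| SD of change (assumed) | dz | Noncentrality, N=99 | Non-significant, N=99 | Non-significant, N=50 (assumed) |
|---|---|---|---|---|
| 40 ms | 0.50 | 4.97 | 0.2% | 7% |
| 50 ms | 0.40 | 3.98 | 2.4% | 21% |
| 60 ms | 0.33 | 3.32 | 9% | 36% |
| 80 ms | 0.25 | 2.49 | 31% | 59% |
| 100 ms | 0.20 | 1.99 | 50% | 72% |

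**Step 3. What a non-significant result leaves open.** The half-width of the 95% interval at N=99 is 1.984/√99 = 0.199 SD. A result just short of significance therefore has an upper limit near 2 × 0.199 = 0.40 SD. That is about 16 ms at SD 40, 24 ms at SD 60 and 32 ms at SD 80.

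**Step 4. The dissociation itself.** Suppose errors and RT had the same true standardised effect, dz = 0.20, and the two tests were independent. Power would be about 0.504 for each. The pattern of errors significant and RT not would then appear with probability 0.504 × 0.496 = 0.25, although the two effects are equal.

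**Step 5. Is an equivalence test feasible at the planned size?** Two one-sided tests at 5% each amount to asking whether the 90% interval lies inside the margin. With a margin of ±20 ms, N=99 and a true change of zero, simulated power is above .99 at SD 40, .98 at SD 50, .90 at SD 60, .59 at SD 80 and .26 at SD 100. If the true mean slowing is 20 ms, the chance of wrongly concluding equivalence is at most 5%.

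**The case against.** The strongest reply is that nothing in the plan depends on this check. It belongs to none of the primary, secondary or exploratory aims, and no covariate or model is conditional on it. The interaction tests use post-alcohol RT and errors whatever it shows. The premise of intact responding rests on cited studies. The app does not need that premise to hold, since it gives feedback on RT slowing as well as on errors. All of this stands, and it keeps the point minor. A reader might infer that the rationale for the app, or the Aim 1 and Aim 2 results, is at risk; the documents do not support that.

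Second, a reader might infer that the plan declares a non-significant result to be proof. It states no decision rule. Reading non-rejection as the route to the RT claim is the natural sense of the sentence, because no other route is offered, but it remains a reading.

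Third, the high SDs may be unrealistic. Targets stay on screen for at most 500 ms and the group-session payment cutoff is 275 ms. In the pilot of the app task, RTs in thirds of one run correlated .89 to .95. If pre and post RT have equal SDs and correlate r, the change SD is the between-person SD × √(2(1 − r)). A change SD of 80 ms would then need a between-person SD of 80/√0.22 = 171 ms at r = .89. At r = .69, the pilot's app-versus-computer correlation, it would need 80/√0.62 = 102 ms. This carries weight but does not settle the matter: the pilot sample had a mean age of 43, the correlations among thirds came from one run, and no alcohol dose is described.

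Fourth, 20 ms is a threshold for one person on one run and not a margin for a group mean. With a mean slowing of 15 ms and SD 40, about 45% of individuals would exceed 20 ms (standard normal probability above 5/40 = 0.125). A ±20 ms equivalence test would still conclude equivalence in about 34% of trials. At a true 10 ms and SD 40 it would do so in about 80%, whereas the t-test is non-significant in 31%. So 20 ms cannot be adopted simply because the app uses it, and non-significance at 10 ms should not be counted as an error under that margin.

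**Conclusion.** The point holds as a minor flaw of inference: the named test cannot support the RT half of the named conclusion, whatever the SD. The practical risk is narrower. At the full N=99, a 20 ms mean slowing would almost never be missed if the SD of change is 50 ms or less, and would be missed in 9% of trials at 60 ms. The risk becomes substantial at 80 to 100 ms (31% to 50%), or if the lab sample shrinks. These figures rest on the assumed SDs, on two-sided .05 and on 20 ms as a benchmark. A reader might infer that the check would usually hide a slowing of that size; at the planned sample that is not so over the lower part of the assumed range.

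**What to change.** 1. Keep the paired t-test for inhibition errors.
2. For RT, report the mean post-dose minus pre-dose change with its confidence interval, and describe a non-significant result as no slowing detected.
3. Conclude that RT was not meaningfully changed only if the 90% interval lies inside an equivalence margin fixed and justified before the data are seen. The app's 20 ms is a candidate, but its use for a group mean needs a stated reason; otherwise choose a tighter margin.
4. State which session or sessions the check covers.

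The cost is a few sentences in Data analyses, with no new data and no change to any primary analysis. The downside is that the RT result may be inconclusive if the SD of change is about 80 ms or more: with a 20 ms margin and N=99, power is .59 at SD 80. A tighter margin or a smaller lab sample would lower it further.

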Risks and potential benefits will be described. Any questions the participant may have will be addressed. If the subject wishes, he/she may take the consent form home (or review the eConsent, if remote) and consider it further before signing. They may also request to speak to anyone on the research team about questions they have. Once the participant has signed the consent, s/he may withdraw consent at any time. This informed consent form will serve as documentation of the major aspects of the consent process. The informed consent form will be signed and dated by the participant, and countersigned and dated by the staff member obtaining

consent. Field-use only participants who are screened entirely remotely will be prompted to sign the ICF electronically using RedCap. A copy of the signed informed consent form will be given to the participant. Informed consent will be obtained prior to performance of any protocol-specific procedures at the in-person screening. A breath alcohol concentration (BrAC) reading will be taken immediately after signing of the informed consent. The informed consent will be considered valid and the in-person screening appointment will proceed only if the participant's BAC = 0.00%. Following the BrAC reading, participants will also complete drug and pregnancy tests (women); timeline followback (TLFB)⁶⁴ for 30-day alcohol/ other substance use; medical history; diagnostic interview³⁶; and will complete the cued go/no-go task. The screen will take approximately 2 hours, and participants will receive up to \$30 via a prepaid debit card.

Eligible participants who are interested in enrolling will be assigned to the earliest possible individual alcohol drinking session. After this individual session, participants may be invited back to complete a group alcohol session on a different day along with two other participants with similar availability. There is a web-based, REDCap questionnaire for participants to complete in conjunction with the in-person screen, however participants complete this questionnaire on their own. However, if participants do not do so between the in-person screening appointment and the individual alcohol drinking session, we will request that participants complete the web-based questionnaire on the day of the individual alcohol drinking session on one of the computers in the research office.

Individual Alcohol Drinking Session:

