Preliminary steps: Participants will be asked not to eat for 3 hours pre-arrival. Alcohol drinking will occur in a bar lab located at Yon Hall North in Ben Hill Griffin Stadium at the University Florida campus. Participants will be brought to the bar or simulated laboratory for the session via study-provided transportation: either a professional service such as taxi or Uber or a UF-owned automobile driven by a UF employee. However, if a participant lives within a 0.5-mile radius of the research facility they may walk to the facility rather than being driven. These participants may be walked home by study staff after the end of the alcohol drinking session. Upon arrival, BrAC must=0.00% and urine tests will be repeated. Participants registering a BAC > 0.00% or with a positive urine test that leads to exclusion will be dismissed immediately and provided transportation directly home by the study. Participants will complete US-THRIVE, an efficacious, brief, web intervention based on M.I. (i.e., personalized feedback on drinking patterns, behavioral strategies, alcohol facts and resources). Before the alcohol administration, participants may be asked to wear the BACTrack Skyn alcohol wristband monitor, which looks like a fitness tracker or wristwatch and can detect alcohol as it evaporates through the skin. Prior to the session, they will be randomized to 1 of the 3 app conditions. The randomization procedure will be managed by a study staff member/collaborator without direct participant contact. Staff working with participants will not know app assignment.

Instructions: After participants learn their app condition, they will view a presentation on the CGNG and how to use their assigned app. They will be told the app is based on a cognitive game and that they will use it 3 times. They will learn that the task is relevant to real-life as moderate amounts of alcohol affect task success and poor performance has been linked to driving problems and risky decisions. [name] has used similar instructions relating alcohol to task performance and pay^{65, 66} and seen a range of alcohol use in lab drinking sessions.

Alcohol administration steps: After completing US-THRIVE and using the app, the participant will be given vodka mixed drinks targeting a BAC of .06% based on sex, height, and weight divided into three parts. The participant will have 10 minutes to complete each drink and after

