Preliminary steps: Participants who are invited back for a group alcohol drinking session will be asked not to eat for 3 hours pre-arrival. Alcohol drinking will occur either in a bar lab or other room located at Yon Hall North in Ben Hill Griffin Stadium at the University of Florida campus. At around 3:45pm, participants will be brought to the bar or simulated laboratory for the session via study-provided transportation: either a professional service such as taxi or Uber or a UF-owned automobile driven by a UF employee (Table 2). However, if a participant lives within a 0.5 mile radius of the research facility they may walk to the facility rather than being driven. At the end of the session, these participants may be walked home by study staff. Upon arrival at 4pm, BrAC (must=.00%) and urine tests will be repeated (Table 2). Participants registering a BAC > 0.00% or with a positive urine test that leads to exclusion will be dismissed immediately and provided transportation directly home by the study. At this appointment, participants will receive an abbreviated version of the instructions on how to use the app and its value (see below). Participants will also complete baseline self-reports and the cued go/no-go task on the app. Before the alcohol administration, participants may be asked to wear the BACTrack Skyn. Each session will be scheduled with 3 people each assigned to a different app, but if 1 cannot participate, the session may still occur. While it is our preference that this appointment occur at 4pm just before the rest of the drinking session activities, if a participant's schedule does not permit it, the 4pm activities may also be scheduled earlier in the day on the day of the session or the day before. In the case of an appointment the day before, the urine drug and pregnancy test will still occur on the day of the session. Payment for this appointment will be \$20 via cash card and will be transmitted on the day of the appointment.

Instructions: The day of the group session participants will be given a brief review of the instructions that were given to them at their individual drinking sessions. Participants will be asked to not share their results on the app with the other participants. Study staff will explain to participants that to incentivize fast, accurate performance (Fig. 2a), they will get \$.10 each

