Impaired control: The *Impaired Control Scale*³³ (*ICS*) consists of three parts including 5 items concerning actual attempts at limiting alcohol consumption (Part 1); 10 items assessing the frequency of past failures at controlling drinking (Part 2) and 10 items assessing beliefs regarding future ability to control drinking (Part 3). Parts 1 and 2 will be administered in this study. The ICS is reliable and has been validated in clinical and community samples. Items are rated on a 0 to 4 scale and summed with higher scores indicating greater difficulty in controlling consumption.

The *Protective Factors Questionnaire* measures frequency of alcohol-related protective strategy use on a 7-point scale. This measure has been used with young adult samples in several studies.

Facets of impulsivity: Impulsivity and risky decision making will be measured using the *UPPS Impulsive Behavior Scale*: a 59-item measure that assesses five subdimensions of impulsivity (premeditation, positive urgency, negative urgency, sensation seeking and perseverance). A *cued go/no-go task*⁶⁰ will be administered during the in-person screening appointment. This is a

8-10 minute computerized task which assesses the ability to inhibit a prepotent response. Subjects are instructed to press a key or inhibit pressing a key based on the colors of the shapes presented. The orientation of the shape (horizontal or vertical) before the color appears signals imperfectly the likelihood that the subsequent stimulus will be “go” or “no-go.” Participants receive feedback regarding their accuracy and speed of response.

In-Person Screening Appointment and at Preliminary Appointment Day of the Sessions:

Self-reported alcohol consumption and smoking: The *Timeline Followback Interview* (TLFB) will be administered at the in-person screening and updated at the preliminary appointment. Participants will be given a blank calendar including memory prompts (e.g., holidays), which covers the designated time interval (the prior 30 days at initial screening) and asked to reconstruct their drinking behavior and smoking over that interval. The TLFB has good test-retest reliability and good validity for verifiable events.

Marijuana use: Participants will be asked on how many days they have used any form or marijuana. Participants will be asked to report on the prior 30 days at the in-person screening appointment and since the in-person screening appointment at the appointment on the day of the session.

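### The Aim 1 regression lets chance imbalance choose its covariates and would usually leave out screening drinking, which is already collected; this affects efficiency and prespecification, not validity

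*Combined protocol and SAP*

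**What the plan says.** In section 6, Data analyses, the combined protocol and SAP describes the Aim 1 model: "The main method will be multiple regression with study condition and sex as predictors". The next sentence adds: "Baseline variables that differ significantly by condition will be covaried". It gives no candidate list, test or threshold, and no rule on when a covariate must be measured. Aim 1b follows a similar strategy. The confirmatory multilevel model adds a random group effect and names no further covariate.

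Under Sample, power & effect size, power is computed without covariates: at d=.89 and α=.025, "the proposed sample of 99 completing the lab session and follow-up period yields .90 power".

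Under Assessments, the TLFB "will be administered at the in-person screening and updated at the preliminary appointment". The screening administration covers the previous 30 days.

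The plan treats Exploratory Aim 1 differently. There, the baseline report of each alcohol outcome and sex enter as covariates whether or not they differ by condition. Only additional covariates depend on an imbalance test.

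The timing of randomisation is described in two ways. The Background and the Overview place it after US-THRIVE, which is completed at the individual session. The Preliminary steps of the Individual Alcohol Drinking Session say: "Prior to the session, they will be randomized to 1 of the 3 app conditions".

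**The concern.** Under randomisation, a significant baseline difference in a pre-randomisation variable is a chance event. A rule triggered by it has two weaknesses:

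- **The primary model is not fixed in advance.** Its covariates are settled only after baseline data have been compared by condition, with an unstated test on an unstated list.
- **It selects on the wrong relation.** A covariate sharpens the comparison if it predicts the outcome. The rule looks at its relation with condition. A prognostic variable that happens to be balanced is left out, and an irrelevant one that happens to be unbalanced is put in.

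Recent drinking is the obvious candidate predictor of how much people drink in the bar lab. It is measured at screening, before randomisation on either description of the timing. Yet it enters the primary model only by accident. At stake are some precision and a primary analysis that can be written down beforehand.

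**Working it through.** **1. Reproduce the stated power.** Inputs from Sample, power & effect size: d=.89, α=.025 per comparison, 33 per condition (99 in total).

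- Non-centrality: .89 × √(33/2) = 3.615.
- Normal approximation, two-sided: Φ(3.615 − 2.241) = Φ(1.374) = .915.
- Noncentral t: .904 on 64 df, .908 on 96 df.

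The plan's .90 is reproduced without any covariate. A one-sided .025 test would give .945 (t), so the two-sided reading fits.

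**2. How often one variable enters.** The threshold is not stated; .05 is assumed. With a three-arm F test, entry is 5% by construction (simulated .048 to .051), so the variable is left out in about 95% of trials. If any of the three pairwise tests suffices, entry is .120 to .123, so it is left out in about 88%.

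**3. What always adjusting would gain.** If the covariate has correlation r with the outcome, the residual SD is multiplied by √(1 − r²). By normal approximation, power = Φ(3.615/√(1 − r²) − 2.241):

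- r=.3: Φ(3.790 − 2.241) = .939, against .915 unadjusted.
- r=.5: Φ(4.174 − 2.241) = .973.

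The table gives simulated power: ordinary least squares, 33 per arm, condition and sex in every model, experimental against control, normal outcome, 40,000 trials per r. The documents do not give r, so all values are assumptions. Monte Carlo error is about √(.904 × .096/40,000) = .0015.

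| r | Unadjusted | Plan's rule, F test | Plan's rule, any pairwise | Always adjusted |
|---|---|---|---|---|
| 0 | .904 | .903 | .903 | .900 |
| .1 | .905 | .905 | .905 | .905 |
| .3 | .903 | .905 | .907 | .927 |
| .5 | .905 | .911 | .918 | .966 |

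The gain from always adjusting is nil at r=.1, .927 − .903 = .024 at r=.3 and .966 − .905 = .061 at r=.5. The plan's rule recovers little of it. If the true effect were smaller, more would be forgone: at an assumed d=.5 and r=.5 (6,000 trials), power is .404 unadjusted, .406 under the F-test rule and .523 always adjusted.

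**4. What happens with many candidates.** The Assessments name about 20 baseline measures, counting each instrument once. The plan does not say how many would be tested. With 20 independent candidates and a .05 F test, at least one enters with probability 1 − .95^20 = .64. Simulated power with 20 independent candidates, one of them prognostic (20,000 trials per cell):

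| r of the one prognostic candidate | Unadjusted | Rule, F test | Rule, any pairwise | That one prespecified |
|---|---|---|---|---|
| .1 | .902 | .889 | .878 | .903 |
| .3 | .905 | .894 | .886 | .926 |
| .5 | .906 | .898 | .896 | .967 |

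The loss against no adjustment runs from .906 − .898 = .008 to .902 − .878 = .024. It arises because the rule picks covariates that overlap with condition. It shrinks in other settings:

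- With 5 candidates, one prognostic, the rule gives .900 to .904 against .904 to .905 unadjusted.
- With 20 candidates, all equally prognostic (intercorrelation .3, joint R² .25), the rule gives .919 to .923, against .903 unadjusted and .927 prespecified.

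**5. Type I error.** Under the rule it was .020 to .027 over all null scenarios, against a nominal .025.

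**The case against.** The strongest reply is that nothing in the plan becomes invalid. The power claim is right as stated, error rates hold, and with a single candidate the rule does not lower power. All of that stands.

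The forgone gain may also be small. Entry requires at least 12 drinking days, four heavy-drinking days and one estimated BAC of .12% in the past 30 days. The outcome runs only from a .06% fixed dose to a .12% cap. The earlier paradigm that the plan cites saw 0 to 3 drinks, though in 20 minutes. All this may compress the correlation between screening drinking and laboratory intake, and below about r=.2 the gain is about a point or less. This stands too; the r=.5 figures are not a forecast.

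The power loss with 20 candidates is likewise conditional. The plan does not say that every instrument will be tested, and many are alcohol-related, so one prognostic measure in 20 is an unfavourable case.

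A reader might infer that the rule admits covariates measured after randomisation, because the group-session text says "Participants will also complete baseline self-reports and the cued go/no-go task on the app" and because, for those who have not yet done it, "we will request that participants complete the web-based questionnaire on the day of the individual alcohol drinking session". The documents do not support that firmly. The group-session self-reports may simply be pre-drink measures, and nothing names them as Aim 1 covariates. If randomisation follows US-THRIVE, a session-day questionnaire could precede it. Participants learn their condition only after arrival, and staff working with them do not know it. What remains is that the descriptions of randomisation timing differ, so the meaning of baseline is not pinned down.

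The reply does not remove the central fact: the covariates of the primary model are left to chance, while Exploratory Aim 1 fixes its baseline alcohol covariates in advance.

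**Conclusion.** The point holds as a matter of efficiency and prespecification, and the change is worth making because it is nearly free. The primary model should not depend on which baseline variables happen to differ by condition, and screening drinking would be omitted in about 88% to 95% of trials at a .05 threshold. At d=.89, naming it is worth nothing at r=.1, about 2 points at r=.3 and about 6 at r=.5. The rule itself costs about 1 to 2 points only with a long list of mostly non-prognostic candidates; with about five, the loss is negligible.

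A reader might infer bias, a raised false-positive rate or an underpowered Aim 1. None of these follows: simulated type I error stays near .025, and the .90 figure never relied on adjustment. The sizes rest on assumed values of r, an assumed entry threshold, an assumed number of candidates and a normal outcome.

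**What to change.** For Aims 1a and 1b, replace the imbalance rule in Data analyses with wording such as:

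> The primary models contain app condition, sex and drinks per drinking day over the 30 days covered by the TLFB at in-person screening. The screening value is used, not the later update. All covariates are measured before randomisation. Adjustment for other baseline variables that differ by condition is a sensitivity analysis only.

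The confirmatory multilevel models should carry the same fixed effects. Drinks per drinking day is an example; the documents do not show which TLFB summary best predicts laboratory intake. What matters is that one is chosen now.

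Reconcile the Background and Overview with the Individual Alcohol Drinking Session text on when randomisation occurs, and define baseline accordingly.

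The cost is wording plus one degree of freedom. The variable is already collected. If it proves uninformative, power goes from .904 to .900, a loss of under one point.
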